The World Health Organization (WHO) has recently defined patient centeredness as a fundamental characteristic for the quality of health care (1). Patient centeredness can be measured through the collection of functional outcomes and quality of life reported by patients, the so-called Patient-Reported Outcome Measures (PROMs). The Organization for Economic Cooperation and Development (OECD) has launched an initiative (called PaRIS Initiative) for the systematic collection of PROMs in patients undergoing elective hip and knee prosthetic arthroplasty 6 and 12 months after surgery (2). Such data is already routinely collected in several OECD member countries that have implemented implant registries (3). The IRCCS Rizzoli Orthopedic Institute (IOR) was selected as a pilot center for the launch of the initiative, whose purpose is to accelerate the adoption and reporting of validated, standardised, internationally-comparable patient-reported indicators, particularly within patient registries. IOR was selected as a pilot center for the launch of the program in Italy because the Institute hosts the Registry of Orthopedic Prosthetic Implantology (RIPO) since 1990 (4). Given that RIPO also includes shoulder implants, the same data will be collected also for patients undergoing shoulder replacement.

OBJECTIVES OF THE STUDY

- 1) To monitor and analyze functional outcomes and quality of life reported by patients undergoing elective hip, knee and shoulder arthroplasty performed at the IOR;
- 2) To identify predictive factors influencing the evolution of patients-reported outcome measures.

STUDY DESIGN

Prospective cohort study.

METHODS

Setting of the study

The study will be carried out at 6 operative units of the IOR (Orthopedic and Traumatological I Clinic, Orthopedic and Traumatological Clinic II, Orthopedic and

Traumatologic Clinic III, Reconstructive Orthopedic Surgery - Innovative Techniques / Revision surgery of hip prosthesis and new implant development, Surgery of the Shoulder and Elbow, Orthopedics-Traumatology and Prosthetic Surgery and of hip and knee replanting). For patients accessing through the “hospitalization-before-surgery” pathway, the enrollment will take place in the specific ambulatory in the month preceding the intervention. The remaining patients will be enrolled directly at the operative Units involved.

Participants

Inclusion criteria:

1. Males and females aged 18-95 years
2. Be on the list for an elective primary arthroplasty of hip, knee or shoulder
3. Availability to sign the informed consent

Exclusion criteria:

1. Severe cognitive impairment
2. To be listed for arthroplasty for musculoskeletal cancer
3. Not eligible for the surgical intervention

Procedures

The study consists of 3 phases:

1. **Baseline:** identification of eligible patients that the meet inclusion criteria. The evaluation will be performed in the pre-hospitalization ambulatory in the month preceding the intervention or in the ward at the time of hospitalization; in this phase it is planned also to:
 - present the study to the patients and collect the informed consents for study participation for the treatment of personal data
 - collect patients' authorization to be contacted by mail or by telephone for the follow-up.

- Administer and collect 2 questionnaires (EQ-5D for all subjects and the joint-specific questionnaire: hip, knee or shoulder).

The baseline includes two different ways of distributing and collecting questionnaires, based on the method of hospitalization:

- For patients in the “hospitalization-before-surgery” pathway (about 90% of the study population), RIPO personnel will go to the pre-admission ambulatory and will distribute and collect informed consents and questionnaires. Patient questionnaires administered to patient not eligible for intervention at a later stage will be destroyed.
- For patients not in the “hospitalization-before-surgery” pathway (about 10% of the population), the RIPO personnel will go directly to the operative units, after checking the day before the scheduled hospitalizations, and will distribute and collect informed consents and questionnaires.

The staff in charge of the distribution and collection of the questionnaires will put their data on the front page of the questionnaire and then they will be transformed into an identification code containing the initials of patients' name and surname followed by a progressive number. This code be used for data entry in the CRF and then to reconcile the patient record with RIPO unique pseudo-anonymized identification code.

2. **6 and 12 months follow up:** the RIPO staff will send a mail containing the same 2 questionnaires described in the baseline phase together with an accompanying letter with the instructions and a pre-paid envelope; the subject will be asked to resubmit the questionnaires. It will be also indicated how to receive direct support by contacting the IOR. In the event that patients - after receiving the package with the follow-up questionnaires - do not send them within 1 month, they will be directly contacted by telephone.
3. **Data collection and processing** will be performed by the RIPO staff and the methodological and statistical support of the biomedical research and health services unit of the University of Bologna.

Questionnaires

Four validated questionnaires will be used in the study. One questionnaire (Euro Quality 5 Dimensions, EQ-5D) for the general assessment of patient's health status will be administered to all the patients in the study (5). Three other joint-specific questionnaires will be administered to patients depending on the surgery procedure they will be undergoing. The joint-specific questionnaires are: Hip disability and Osteoarthritis Outcome Score - Short Form (HOOS-PS) for patients undergoing hip replacement (6); Knee injury and Osteoarthritis Outcome Score - Short Form (KOOS-PS) for patients undergoing knee replacement (7); the American Shoulder and Elbow Surgeons Standardized Shoulder Assessment Form (ASES), for patients undergoing shoulder implants. This last questionnaire will be administered in a modified version that does not include the assessments performed by the orthopedic surgeon (8).

ENDPOINTS

The outcomes of interest are functional outcomes and quality of life, measured through the total scores and the subscales of the administered questionnaires.

In particular, for the joint-specific functional scales the total score will be used, while for the EQ-5D the scores of the single dimensions will be used, together with a total VAS score on a 0-100 scale, that measures the overall health status.

The type of intervention will be used to stratify patients into three groups (hip, knee and shoulder).

The socio-demographic and clinical variables of interest, such as sex, age, comorbidity, and patient's clinical history, will be extracted from the clinical records and the data recorded in the RIPO.

SAMPLE SIZE

All patients hospitalized for elective hip, knee and shoulder prosthetic surgery at the 6 participating Operative Units will be included in the study. Based on the number of surgical procedures (i.e. implants) carried out in 2016, it is planned to recruit a total of 1700

patients, of which 1100 with hip replacement, 500 with knee replacement and 100 with shoulder replacement. A 10% rejection rate and a 40% follow-up loss are expected.

QUANTITATIVE VARIABLES

The quantitative variables of the study, which include the total scores of the scales and the subscales of the questionnaires, will be treated as such in the analyses and therefore not transformed.

STATISTICAL ANALYSES

Statistical analyses will be performed by the RIPO biostatistician in collaboration with the biostatistician of the methodological and statistical support unit for biomedical and on health services research of the Department of Biomedical and Neuromotor Sciences of the University of Bologna.

To analyze the evolution of the functional outcomes and quality of life of patients at 6 and 12 months from the surgery according to the type of intervention - and to identify predictive factors that influence this evolution - generalized estimation equations (GEE) and structural equation models (SEM) will be used. These techniques allow to obtain robust estimates even in the presence of missing data. We estimate an attrition rate of about 40% of cases, and non-compliance in resubmitting the questionnaires is hypothesized not to be linked to a systematic reason (for example the lower severity of patients). Therefore the missing data is to be considered completely random (MCAR).

Sensitivity analyses will be performed to assess whether the hypothesized mechanism of data loss at follow-up is supported by the data, or if alternative mechanisms need to be considered.

STUDY DURATION AND TIMELINE

The study will have an overall duration of 30 months and will be considered in any case completed 6 months after the recruitment target is achieved.

The study timeline is the following:

- Months 1-12: Selection and enrollment of the patients and database implementation.
- Months 6- 24: Follow up (6 and 12 months) and database implementation.

- Months 24-30: Analysis of data and dissemination of results.

The approval of the Ethics Committee will be considered as the start date of the study.

Study start date: 1/1/2019 (after approval by the Ethics Committee)

Enrollment start date: 1/1/2019

End date of study: 30/06/2021

CONSENT TO PARTICIPATE AND PRIVACY

Participation in the study is exclusively on a voluntary basis. Each subject will obtain detailed information regarding the nature and the procedures of the project and its purposes. All patients must sign a written consent before being included. Sensitive data will be processed according to the regulations in force by the study manager. Furthermore, participants can withdraw their consent to participate at any time, without any consequence.

The protection of personal information provided by the subjects will be in accordance with current legislation on the protection of personal data. In line with international data protection legislation, the following measures will be taken:

- The access to the database will be restricted to authorized persons;
- The paper material will be stored in dedicated lockable cabinets not accessible to unauthorized parties;
- The questionnaires and all paper data will also be archived in digital format at the medical technology laboratory with private access through a password.

ETHICAL PRINCIPLES

The study protocol and related documents will be sent before starting the study to the competent authorities and to the ethics committee for approval. The responsible investigator will ensure that the study is conducted in accordance with the Helsinki Declaration in its most up-to-date version (Fortaleza, October 2013), as well as with all national and international legislation applicable to clinical research.

The protocol has been written and the study will be conducted according to the principles of ICH-GCP (ref: <http://www.emea.eu.int/pdfs/human/ich/013595en.pdf>).

FINAL REPORT AND PUBLICATION OF RESULTS

The principal investigator agrees to produce a final report, to publish all the data collected as described in the protocol and is responsible for data integrity and to ensure that data are reported responsibly and consistently. The publication of data from the present study will take place independently of the results.

The transmission or dissemination of study results through scientific publications and / or public presentations will be based on anonymous data and on statistical processing.

REFERENCES

1. WHO 2018. Delivering quality health services: a global imperative for universal health coverage. Geneva: World Health Organization, Organisation for Economic Co-operation and Development, and The World Bank; 2018. Licence: CC BY-NC-SA 3.0 IGO.

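### Does leaving the role of the pre-operative score unstated in the GEE and SEM undermine the search for predictive factors?

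*Combined protocol and SAP*

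**What the plan says.** The combined protocol and SAP sets as its second objective "To identify predictive factors influencing the evolution of patients-reported outcome measures". At baseline (Procedures) staff are to "Administer and collect 2 questionnaires (EQ-5D for all subjects and the joint-specific questionnaire: hip, knee or shoulder". At 6 and 12 months "the RIPO staff will send a mail containing the same 2 questionnaires described in the baseline phase". Each scale is therefore measured up to three times.

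Under Endpoints, "The outcomes of interest are functional outcomes and quality of life, measured through the total scores and the subscales of the administered questionnaires". Neither a change score nor a baseline-adjusted score is named. The candidate explanatory variables are "The socio-demographic and clinical variables of interest, such as sex, age, comorbidity, and patient's clinical history", an open list that does not name the baseline score.

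Under Statistical Analyses the purpose is "To analyze the evolution of the functional outcomes and quality of life of patients at 6 and 12 months from the surgery", and the same sentence ties the predictive factors to that evolution. For this, "generalized estimation equations (GEE) and structural equation models (SEM) will be used". No outcome vector, predictor-by-time term or baseline covariate is given. The sensitivity analyses promised there concern the mechanism of data loss only.

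**The concern.** Two models fit the analysis sentence. One takes the scores at 0, 6 and 12 months as the outcome and reads a predictor's effect from its interaction with time, which is an effect on change. The other takes the 6- and 12-month scores as the outcome with the pre-operative score as a covariate, which is an effect among patients with the same starting score. The word for evolution points to the first, while naming only 6 and 12 months leaves room for the second.

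With no randomisation, age, sex or comorbidity may be related to the pre-operative score, and the two effects then differ. A group that starts worse and stays equally worse shows no effect on change but a negative effect given its starting score. If the choice were made after seeing the data, the factors reported under the second objective, and even the direction of an effect, could depend on it.

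**Working it through.** **The plan's own figure.** The Sample Size section plans 1100 hip + 500 knee + 100 shoulder = 1700 patients, which agrees with the stated total. It gives no test level, power, effect size or SD, so there is no power calculation to reproduce.

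**Patients with follow-up.** The section states that "A 10% rejection rate and a 40% follow-up loss are expected". Applying both rates:
- hip: 1100 × 0.9 × 0.6 = 594
- knee: 500 × 0.9 × 0.6 = 270
- shoulder: 100 × 0.9 × 0.6 = 54

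If the planned numbers are already net of refusals, hip is 1100 × 0.6 = 660.

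**Assumptions not in the documents.** Equal SDs (set to 1), a factor present in half the patients, one follow-up visit, a two-sided 5% test, r from 0.2 to 0.7, and d from 0.1 to 0.3 SD.

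**Gap between the two effects.** Let the factor group differ by −d at baseline and by f at follow-up.
- Effect on change: f + d
- Effect given the starting score: f + rd
- Gap: (1−r)d

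At d = 0.3 the gap is 0.24, 0.18 and 0.09 SD for r = 0.2, 0.4 and 0.7. It is zero if d = 0 or r = 1. The signs are opposite when f lies between −d and −rd.

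**Standard errors.** With n followed patients, SE = √(4V/n). For change using all baselines with an efficient working correlation, V = (1−r²) + 0.6(1−r)². For the adjusted model, V = 1−r². At r = 0.4 these are 1.056 and 0.84. In the hip group:
- change: √(4 × 1.056/594) = 0.084
- adjusted: √(4 × 0.84/594) = 0.075

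**Chance of significance when the other effect is exactly zero, r = 0.4** (normal approximation):

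| Group | d (SD) | Gap (SD) | Change model, conditional effect zero | Adjusted model, change effect zero |
|---|---|---|---|---|
| Hip, 594 | 0.3 | 0.18 | 57% | 67% |
| Hip, 594 | 0.2 | 0.12 | 30% | 36% |
| Hip, 594 | 0.1 | 0.06 | 11% | 13% |
| Knee, 270 | 0.3 | 0.18 | 30% | 36% |
| Knee, 270 | 0.1 | 0.06 | 8% | 8% |
| Shoulder, 54 | 0.3 | 0.18 | 10% | 11% |

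The model whose own effect is zero rejects in 5%. For hip at d = 0.3, moving r from 0.2 to 0.7 takes the first percentage from 71% to 31% and the second from 85% to 34%. At d = 0.1 and r = 0.7 both are 8%.

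**Check with both follow-up visits.** In 400 simulated data sets (660 hip patients without missing values, all correlations 0.5, a steady 0.3 SD deficit), the GEE change term averaged −0.003 and was significant in 5%. The baseline-adjusted term averaged −0.152 and was significant in 77%. The divergence is therefore not an artefact of using one visit.

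**The case for a change.** The strongest case for a change is that nothing in the document fills the gap. Naming GEE and SEM does not settle it, since either can hold the baseline score in either role. Leaving scores untransformed concerns their scale, and the planned sensitivity analyses address missing data. A sentence or two, with no new data, would remove the choice. If d is near 0.3 SD, the hip and knee results could name different factors under the two models. All of that stands as a description.

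It falls short of showing a fault. The text is not evenly balanced: the factors are tied to the same evolution as the first objective, the instruments are repeated, and GEE is a repeated-measures method. Neither model is wrong, and no better method is on offer. The most one could ask is that the team write down its choice. Reporting the second model as a sensitivity analysis would not help: it estimates a different quantity, and disagreement is expected for any factor related to baseline.

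Two supporting arguments are weaker than they look. First, a precision gain from adjustment equivalent to 11–40% more patients holds only for an efficient working correlation, which the plan does not specify. Under working independence V for change is 1.6 − 1.2r, and the gain is 42%, 33% and 49% at r = 0.2, 0.4 and 0.7. That comparison also matters only when the factor is unrelated to baseline, where the two effects coincide. Second, the role of baseline does not by itself fix who contributes: an SEM fitted by full-information likelihood can keep baseline-only patients and still estimate the conditional effect.

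**Conclusion.** The omission is genuine and the (1−r)d gap is correct, but this is missing detail and not an error in the plan. The natural reading is change across the three measurements. An analyst who instead adjusts for the starting score also answers a legitimate question, and the fitted model shows which quantity was estimated. The planned recruitment and data collection are the same either way.

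The practical size is uncertain. It could alter which factors are named in the hip and knee groups if a factor's baseline difference is near 0.3 SD. It has little effect near 0.1 SD, or in the shoulder group. These statements rest on assumed d and r, equal SDs, an evenly split factor and a 5% test. The plan states none of these, and the normal SD-unit model may not suit the single EQ-5D dimension scores. In an observational cohort with no stated confirmatory hypothesis, the choice can be left to the analysts.

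### Does the shoulder (ASES) predictor GEE, on about 100 patients, need a standard-error method named in the plan to control false positives?

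*Combined protocol and SAP*

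**What the plan says.** Under Questionnaires, the joint-specific instrument for the shoulder is "the American Shoulder and Elbow Surgeons Standardized Shoulder Assessment Form (ASES), for patients undergoing shoulder implants". ENDPOINTS stratifies the analysis by joint, so an ASES model cannot borrow hip or knee patients. The ASES is completed at baseline (Procedures) and again at 6 and 12 months.

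SAMPLE SIZE takes the numbers from 2016 surgical volume: 1700 in total, "of which 1100 with hip replacement, 500 with knee replacement and 100 with shoulder replacement". It adds: "A 10% rejection rate and a 40% follow-up loss are expected".

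STATISTICAL ANALYSES states the method for objective 2: "to identify predictive factors that influence this evolution - generalized estimation equations (GEE) and structural equation models (SEM) will be used". It says of both methods: "These techniques allow to obtain robust estimates even in the presence of missing data". There, robust refers to missing data and not to a variance estimator. Candidate predictors are given as an open list in ENDPOINTS: "The socio-demographic and clinical variables of interest, such as sex, age, comorbidity" and clinical history. The plan gives no standard-error method, working correlation, reference distribution, significance level or number of predictors. It assigns the analysis to the registry's biostatistician, working with a university biostatistician.

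**The concern.** The sandwich variance commonly used with GEE is justified by a large number of independent clusters, which here are patients. With few patients and many model terms the residuals are shrunk by the fit. The sandwich is then too small, and Wald tests reject too often.

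The shoulder group is the one stratum where this could matter. Its 100 patients fall to 54 to 60 with follow-up, and the four predictor types that the plan names could expand into more terms once comorbidity and clinical history are coded. If the analysts used an uncorrected sandwich with a normal reference, some shoulder factors with no effect would be reported as predictive more often than the nominal rate, and 95% intervals would be too narrow. Identifying predictive factors is the second of the study's two objectives, so silence on the standard error looks like an omission worth repairing.

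**Working it through.** **Plan's own figure.** 1100 + 500 + 100 = 1700, as printed. The size comes from surgical volume, so there is no power or type I error figure to reproduce.

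**Shoulder counts.** The plan does not say whether 100 counts patients approached or enrolled.
- If approached: 100 × 0.9 = 90 enrolled; 90 × 0.6 = 54 with follow-up.
- If enrolled: 100 × 0.6 = 60 with follow-up.
- Share of cohort: 100/1700 = 5.9%.

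Baseline scores exist for everyone enrolled, so a model of change uses 90 to 100 patients.

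**Simulation under the null.** Assumptions not in the plan: two-sided 5% level, Gaussian outcome, exchangeable working correlation, true within-patient correlation 0.6, half the predictors binary, and 40% of patients with baseline only. The terms are an intercept, two time terms, k main effects and k predictor-by-post terms. That is 3 + 2k: 11 terms for k = 4 and 19 for k = 8. Rejection rates for the predictor-by-post terms, averaged over predictors (4000 data sets per setting):

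| Predictors | Uncorrected sandwich, 90 enrolled | 100 enrolled |
|---|---|---|
| 1 | 5.8% | 6.3% |
| 2 | 6.6% | 7.1% |
| 4 | 7.7% | 7.4% |
| 8 | 8.6% | 7.9% |

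Hip and knee sizes (450 to 1100 enrolled) gave 5.1 to 5.6%.

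**Separate simulation, correlation 0.5** (2000 data sets per setting, uncorrected sandwich, normal reference):
- Predictor-by-time model: 7.4 to 7.8% with 4 predictors, 8.2 to 9.1% with 8.
- Same model, each follow-up visit missed independently (90 enrolled): 6.6% with 4, 8.0% with 8.
- Main effects only, 4 to 10 predictors: 6.1 to 8.3%.
- Follow-up scores adjusted for baseline (54 to 60 patients): 7.7 to 8.5% with 4, 9.3 to 9.6% with 8, 10.3 to 10.7% with 10.

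**Other standard errors that the plan equally permits.**
- Kauermann-Carroll correction with t: 5.0 to 6.4% across the settings in the table. Intervals are about 6 to 9% wider with 4 predictors and 10 to 13% with 8.
- Model-based standard errors with t, 4 to 8 predictors: 4.7 to 5.5% at correlation 0.3 to 0.6, and 6.3 to 7.5% at 0.8.
- Sandwich variance multiplied by N/(N − p), with t on N − p degrees of freedom. This can be approximated from the table by treating the uncorrected statistic as normal with standard deviation s.
  - N = 90, p = 11: a rate of 7.7% implies s = 1.960/1.768 = 1.108. The new threshold is √(90/79) × 1.990 = 2.125. Then 2.125/1.108 = 1.917, a rate of about 5.5%.
  - N = 90, p = 19: a rate of 8.6% implies s = 1.960/1.717 = 1.142. The threshold is √(90/71) × 1.994 = 2.245. Then 2.245/1.142 = 1.966, a rate of about 4.9%.

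**Consequence, if nothing is corrected.** Extra expected false flags per ASES model, from the table:
- 4 null predictors: 4 × (0.074 to 0.077 − 0.05) = 0.10 to 0.11.
- 8 null predictors: 8 × (0.079 to 0.086 − 0.05) = 0.23 to 0.29.

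For comparison, testing at exactly 5% already gives 4 × 0.05 = 0.20 and 8 × 0.05 = 0.40.

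**The case for a change.** The strongest case for a change is that the arithmetic is sound and reproducible, the plan excludes nothing, and the remedy is a sentence. Two independent simulations agree on roughly 7 to 9% for models of change with four to eight predictors. Four predictor types are already named, so eight terms is not far-fetched. Shoulder is one of three declared strata with its own instrument, and results are to be published whatever they show. Switching from a normal to a t reference without correcting the sandwich still left about 6 to 10%. Model-based errors are not a sure refuge if the correlation is high.

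Most of this stands as a description of what could happen. It does not show that the plan will produce the error. The rate follows from an uncorrected sandwich, a 5% level, a predictor count, a model form and a missing-visit pattern, none of which the plan states. It also names GEE and SEM together without assigning the ASES analysis to either. Nor is the remedy free. With eight predictors, simulated power for a 0.55 SD difference in change falls from 77/81% (90/100 enrolled) to 72/76% with Kauermann-Carroll and to 66/71% with the more conservative Mancl-DeRouen correction. Part of that fall is inflated error being removed. Which correction to accept is a judgement best made once the number of usable patients and terms is known.

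**Conclusion.** The concern describes a missing detail, not an error, and no change follows. If an uncorrected sandwich with a normal reference were used for the shoulder group, per-test type I error would be about 6 to 9% in models of change with up to eight predictors. It would reach about 9 to 11% only with eight to ten predictors in a model of follow-up scores alone. These figures rest on an assumed 5% level, Gaussian outcomes, a within-patient correlation of 0.5 to 0.6, and assumed predictor counts and loss patterns.

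An excess of 1 to 4 points per test for most model choices, in an exploratory analysis of about 6% of an observational cohort, does not threaten the study's conclusions. There is no treatment comparison and no decision rule tied to a p-value. Hip and knee results are essentially unaffected. A statistician fitting a GEE to under 100 patients would ordinarily choose a small-sample correction and limit the number of terms. The plan leaves room for both and names the biostatisticians who will do it. Whether 1700 counts patients approached or enrolled is a wording point: both readings lead to the same conclusion.

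### With about 40% attrition expected, MCAR is assumed on a hypothesis without supporting data, and no analysis is named for use if the planned check contradicts it

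*Combined protocol and SAP*

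**What the plan says.** Under STATISTICAL ANALYSES, for change at 6 and 12 months and for its predictors, "generalized estimation equations (GEE) and structural equation models (SEM) will be used". The next sentence says of both: "These techniques allow to obtain robust estimates even in the presence of missing data". The same paragraph puts attrition at about 40%, in agreement with SAMPLE SIZE ("A 10% rejection rate and a 40% follow-up loss are expected"). It gives one basis for the mechanism, that "non-compliance in resubmitting the questionnaires is hypothesized not to be linked to a systematic reason", with lower severity as its own example of such a reason. It then concludes: "Therefore the missing data is to be considered completely random (MCAR". The following paragraph plans sensitivity analyses to assess "whether the hypothesized mechanism of data loss at follow-up is supported by the data, or if alternative mechanisms need to be considered".

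Three other places bear on the point:
- ENDPOINTS uses total scores for the joint-specific scales and the VAS, while "for the EQ-5D the scores of the single dimensions will be used". It also lists sex, age and comorbidity among the variables taken from clinical records and the registry.
- Procedures, baseline phase: "Administer and collect 2 questionnaires (EQ-5D for all subjects and the joint-specific questionnaire", so baseline scores exist for enrolled patients.
- Procedures, follow-up phase: patients who have not replied within a month are telephoned.

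The document does not state a GEE working correlation, any weighting, whether the baseline score is an outcome or a covariate, the SEM estimator, an imputation method, an MNAR analysis, or what happens if MCAR is not supported.

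**The concern.** MCAR is the strongest of the usual missing-data assumptions, and here it covers about two patients in five. It follows from a hypothesis for which the plan offers no pilot figure, registry experience or citation. The check that follows has no stated consequence. If returners and non-returners differ at baseline, the replacement analysis would be chosen after the data were seen. If they do not differ, MNAR is still not excluded.

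The robustness sentence does not close the gap, because whether GEE and SEM tolerate a failure of MCAR depends on choices the plan leaves open. Objective 1, the course of function and quality of life after surgery, is the most exposed, since it rests on mean changes. Objective 2, on predictors, is less exposed: return driven only by correctly modelled covariates leaves predictor effects unbiased.

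**Working it through.** **1. The plan's figures.** 1100 + 500 + 100 = 1700, as stated. The 40% has no derivation to reproduce. Expected returners are 1700 x 0.60 = 1020 (hip 660, knee 300, shoulder 60). If the 10% refusal also comes out of the 1700, they are 1700 x 0.90 x 0.60 = 918 (594, 270, 54). The text allows either reading.

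**2. Conditions for validity.** Unweighted GEE sums the residuals of returned questionnaires. These have mean zero in general only if return is independent of the scores given the modelled covariates. A baseline score treated as one of the repeated outcomes does not count as such a covariate. SEM by full-information likelihood is valid under MAR when the variables that drive return are in the model; SEM on complete cases does not have this property.

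**3. Illustration of size.** The documents give no SD, correlation or return pattern, so all of the following are assumptions:
- score correlations 0.40 (baseline to 6 months), 0.70 (6 to 12) and 0.35 (baseline to 12);
- 75% return at 6 months and 60% at 12;
- normal scores, with 1,000,000 simulated patients per row (Monte Carlo SE about 0.001).

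The second figure in each pair allows non-monotone return: 70% of 6-month returners and 30% of non-returners send the 12-month form. Entries are the bias of the 12-month mean change in SD, monotone / non-monotone.

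| Return OR per SD of baseline / 6-month score | Independence GEE, no baseline covariate | Independence GEE, baseline covariate | Exchangeable GEE |
|---|---|---|---|
| 1 / 1 (MCAR) | 0.000 / 0.000 | 0.000 / 0.000 | 0.000 / 0.000 |
| 1.25 / 1.25 | 0.066 / 0.077 | 0.026 / 0.034 | 0.000 / 0.005 |
| 1.5 / 1.5 | 0.113 / 0.129 | 0.046 / 0.058 | 0.001 / 0.007 |
| 2 / 2 | 0.173 / 0.196 | 0.078 / 0.096 | 0.006 / 0.017 |
| 2 / 1 | 0.097 / 0.099 | 0.000 / -0.001 | -0.030 / -0.029 |
| 1 / 2 | 0.090 / 0.117 | 0.073 / 0.094 | 0.033 / 0.044 |

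Full-information likelihood was within 0.001 of zero in every row. The small exchangeable bias at 2 / 2 is close to the sum of the two single-score rows (-0.030 + 0.033 = 0.003; -0.029 + 0.044 = 0.015), so it reflects cancellation and not a guarantee. With three other correlation sets, exchangeable GEE reached 0.027 when both scores drove return and 0.076 when only the 6-month score did; likelihood stayed within 0.002.

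At 6 months, independence GEE without the baseline covariate gave 0.022, 0.040 and 0.064 at OR 1.25, 1.5 and 2.

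**4. Scale.** For 990 hip patients (1100 x 0.9), the simulated SE under independence GEE was 0.043 to 0.047 SD, so the 95% half-width is 1.96 x 0.043 to 1.96 x 0.047 = 0.08 to 0.09 SD. With 1100 enrolled it is about 5% smaller, since sqrt(990/1100) = 0.95.

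**5. MNAR.** When return depends on the current score (OR 1.25, 1.5, 2; non-monotone), likelihood is biased too: 0.062, 0.111, 0.179. A delta analysis shows the sensitivity directly: shift = 0.40 x delta, so 0.40 x 0.1 SD = 0.04 SD.

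**6. Predictor slope, true value 0.300.**
- Covariate-only return, OR 2: 0.299 to 0.300.
- Earlier-score return, OR 1.25 to 2 (monotone): independence GEE 0.295 to 0.266, likelihood 0.300 to 0.299.
- MNAR, OR 1.25 to 2 (non-monotone): independence GEE 0.296 to 0.267, likelihood 0.297 to 0.277.

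**The case against.** The plan can be read as coherent: it names the methods, states the mechanism under which unweighted GEE is valid, and commits to checking it. A reader might infer that robustness is claimed with no condition at all. That goes too far, because the MCAR statement and the check follow directly. What stands is that the stated condition is unsupported and that nothing is prescribed if it fails.

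A reader might also take 0.20 SD as the bias to expect. That figure needs an independence structure, no baseline score in the model and a strong dependence of return on both earlier scores; the plan specifies none of these. Under the main assumptions exchangeable GEE stays well below the hip half-width, and the planned SEM would already be valid under MAR if fitted by full-information likelihood. This objection largely holds and limits the point to a gap in specification.

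The telephone contact deserves credit as a measure that may reduce loss, but it does not say how the remaining gaps are analysed, and the 40% may already allow for it. Finally, this is an observational cohort with no stated hypothesis test, which lowers the severity.

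**Conclusion.** The point holds as a specification gap that should be fixed; it does not invalidate the study. The text establishes that MCAR is assumed at about 40% attrition without supporting data, that the check leads to no named analysis, and that the robustness sentence is true only under conditions the plan does not secure.

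Size and direction cannot be known from the documents. Under the assumptions above, with return depending on both earlier scores, bias in the 12-month mean change runs from about 0.00 (full-information likelihood), through at most about 0.02 SD (exchangeable GEE; 0.03 to 0.04 in absolute size if one earlier score alone drives return), to 0.07 to 0.20 SD (independence GEE without the baseline score). The result therefore turns on choices not yet made.

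Two stronger conclusions are not supported. Nothing shows that return does depend on scores, so the results cannot be called biased. Nor are the predictor analyses undermined: in simulation their slopes moved modestly, and only when return depended on earlier or unreturned scores.

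**What to change.** 1. Replace MCAR with MAR given baseline score, any returned 6-month score, age, sex, comorbidity and joint. Limit the robustness sentence to its conditions: for unweighted GEE, MCAR or return depending only on correctly modelled covariates; for SEM under MAR, a suitable estimator.
2. Make the already planned SEM, fitted by full-information likelihood with the baseline score and all returned scores, the main analysis for the joint scores and EQ VAS. For the single EQ-5D dimensions, use multiple imputation with baseline and any returned follow-up scores in the imputation model; this also handles a missed 6-month form followed by a returned 12-month form. Keep models simple in the shoulder group, with about 54 to 60 expected returners.
3. Keep the mechanism check and add one delta-adjusted MNAR sensitivity analysis, reported in steps of 0.1 SD (0.04 SD each in the 12-month mean at 40% loss).

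The cost is analysis-plan wording and some extra programming and analysis. No new data are needed, since the questionnaires and covariates are already collected. Precision should hardly change for the joint scores and EQ VAS: with 990 simulated patients the SE was 0.040 to 0.045 SD for likelihood and 0.040 to 0.044 for exchangeable GEE.
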